If you uploaded a separate research protocol document in the 'Research Protocol' page, cite the applicable section and page numbers from that document in the answer boxes below.

- 1 * Provide the rationale and sample size calculations for the proposed target population:

Statistical and power analyses: Hypothesis 1a (larger or faster improvement in Nicotine than Placebo Group): Assuming training effects are linear with time, we will conduct an intention to treat (ITT) analysis by fitting the mixed model regression for repeated measures OCM= time+ treatment+ treatment x time, with time as a continuous measure. The treatment x time interaction estimates the difference between treatment groups in OCM rate of change (slope). Although we will include subjects with partial data, the effect size detectable was estimated conservatively⁷⁸ by: $d = [2(z_a + z_b)2(1-r)/bnVar(t)]/2$, where d = (difference in slopes)/SD(OCM), r = within-subject correlation of OCM, $b=4$ visits per subject, n = number of completers per group, $Var(t)=0.185$ is the within-subject variance of the visit times, and $z_a=1.96$ and $z_b=0.84$ for two-sided $\alpha=0.05$ and power=0.80. With $n=20$ completers per group, $d=0.56$ (a medium effect size) will be detectable for $r=0.7$ consistent with the high ICC of the MCCB, the primary OCM. To explore differences in treatment effects between MCCB domains, we will employ the mixed model for repeated measures: T-score= domain+ treatment+ time+ interactions. In particular, the domain x treatment x time interaction assesses variation among domains in the magnitude of the treatment effects on change slopes in OCM scores. In secondary analyses to guide the design of future studies, we will fit a model in which time is treated as a categorical measure unconstrained by a linear fit to explore different learning scenarios such as a more rapid initial acquisition but similar ceiling. In this model, we will add week 14 data to examine Hypothesis 1b (persistence of improvements after training ends), comparing treatment groups on the difference between week 14 and 10. Other exploratory analyses: 1) Smoking status (smoker, never-smoker) is added as an exploratory between-subject factor. 2) A further regression will explore differences between treatment groups in two compliance measures, the cumulative percentage of missed training sessions and lozenge administrations until each OCM time point. If treatment groups differ on compliance, we would include time-dependent compliance as a mediator of treatment effects. A descriptive analysis to support Hypothesis 1a will compare the percentage of participants in each group that achieves clinically significant improvement in MCCB composite scores (6 points from baseline adjusted for practice effects, see above) at each OCM time point.

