
Hypothesis 2a (training progress within nicotine vs. placebo sessions): For those adaptive exercise parameters for which progress is stated at the end of each session, we will compare nicotine - placebo differences on within-session progress, averaged over 20 lozenge-sessions, between treatment groups using a t-test. Power is estimated from the formula⁷⁸ $d = [2(z_a + z_b)2(1-(b-1)r)/bn]$, where d = (difference in average change)/SD(change within 1 session), $b=20$ visits per subject, and other terms are defined as above. For $n=20$ completers per group, we would have power=0.80 at two-sided $\alpha=0.05$ to detect $d=0.51$ (a medium effect size) for $r=0.3$. r is estimated based on each exercise being short and of potentially low reliability. To test Hypothesis 2b (persistence of nicotine-induced improvements beyond the presence of nicotine), we will analyze within-session progress on no-lozenge sessions. If progress made in the nicotine sessions does not persist, we would expect a performance decrement in subsequent no-lozenge sessions (Tue, Fri), whose difficulty levels begin where the previous session left off. If progress made under nicotine does persist, we would expect no decrement and progress comparable to no-lozenge sessions in the placebo group.

To achieve 20 completers per group, we expect having to enroll 25 subjects per group into the training and having to screen approximately 70 subjects in total.

Please note that screening is part of the study protocol. Thus, we expect to consent 70 subjects.

- 2 * Provide the plan for data analysis. Include in the description the types of comparisons that are planned (e.g., comparison of means, comparison of proportions, regressions, analysis of variance, etc.), which is the primary comparison/analysis, and how the analyses proposed will relate to the primary purposes of the study:

Please see above. The sample size calculation is closely related to the planned analyses.

ID: VIEW4E02806052800

Name: v2_Sample Size and Data Analysis

View: v2_Sharing of Results

Sharing of Results

- 1 * Describe whether results (study results or individual subject results, such as results of investigational diagnostic tests, genetic tests, or incidental findings) will be shared with subjects or others (e.g., the subject's primary care physicians) and if so, describe how it will be shared:

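### The primary model forces the time trend shared by both arms onto a straight line; if that trend is front-loaded, the slope test loses a little power, and a categorical visit effect would prevent this at almost no cost

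*Combined protocol and SAP*

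**What the plan says.** All references are to Sample Size and Data Analysis, item 1, of the combined protocol and SAP, unless stated.

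- **Primary model.** The intention-to-treat analysis for Hypothesis 1a is a repeated-measures mixed model, "OCM= time+ treatment+ treatment x time, with time as a continuous measure". It is introduced with the condition "Assuming training effects are linear with time". The treatment x time term is the test. No covariance structure is named.
- **Non-linear learning.** A secondary model with categorical time, intended to inform later studies, is planned "to explore different learning scenarios such as a more rapid initial acquisition but similar ceiling".
- **Practice effects.** These appear only in a descriptive responder analysis, whose threshold is "6 points from baseline adjusted for practice effects".
- **Missing data.** Subjects with partial data stay in the analysis. On attrition the plan says: "To achieve 20 completers per group, we expect having to enroll 25 subjects per group into the training". It does not discuss a difference in dropout between arms.
- **Visits.** Outcomes are measured at weeks 0, 4, 7, 10 and 14 (Justification, Objective, & Research Design, item 2). The power formula uses four visits per subject, and week 14 enters only the secondary model.

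**The concern.** Continuous time does two jobs in this model. It defines the treatment contrast (a difference in slopes), and it also fixes the shape of the change that both arms share. The first is a deliberate choice and is not questioned here. The second is a restriction that the treatment question does not need.

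Practice on a repeated battery, and training gains that come early and then level off, would bend the shared trend in both arms alike. A straight line cannot follow that bend.

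- **Precision.** The lack of fit goes into the residual, the estimated standard error of the slope difference grows, and power falls.
- **Bias.** If one arm loses more people after week 4, its early leavers contribute only the steep first segment. Part of the shared bend then appears as a slope difference.

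With 20 completers per group and a calculation aimed at exactly 80% power, even a small avoidable loss is worth removing.

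**Working it through.** **Inputs from the documents.** Weeks 0, 4, 7, 10 (scaled t = 0, 0.4, 0.7, 1.0); n=20 completers per group from 25 enrolled; r=0.7; two-sided alpha 0.05; power 0.80 (z = 1.96 and 0.84); Var(t)=0.185; b=4.

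**Assumptions, not in the documents.** A shared gain of 0.5 SD by week 10, with one of two shapes: (A) a 3-week exponential scaled to 0.5 at week 10, giving 0, 0.382, 0.468, 0.5; or (B) complete by week 4, giving 0, 0.5, 0.5, 0.5. Covariance is exchangeable, so the residual variance is 1-r = 0.3.

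**1. The plan's own figure.** d = sqrt[2(1.96+0.84)²(1-r)/(b n Var(t))] = sqrt[2 x 7.84 x 0.3/(4 x 20 x 0.185)] = 0.564, so the stated 0.56 is reproduced.

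For the actual visit times the sum of squares is 0.5475, not 4 x 0.185 = 0.74. The SE of the slope difference is then sqrt[2 x 0.3/(20 x 0.5475)] = 0.234, and 80% power corresponds to 2.80 x 0.234 = 0.655 SD. That is a separate matter. Here it only sets the effect at which nominal power is 80%.

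**2. Lack of fit.** For B, the total sum of squares about the mean is 0.1875. The cross-product with time is 0.5 x (-0.125 + 0.175 + 0.475) = 0.2625. The line explains 0.2625²/0.5475 = 0.1259, leaving 0.0616 per subject. The same steps for A leave 0.0245.

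**3. Residual inflation.** Divide by 3 within-subject degrees of freedom and by 0.3:

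| Curve | Residual variance | SE factor k |
|---|---|---|
| A | 0.0245/0.9 = +2.7% | 1.014 |
| B | 0.0616/0.9 = +6.8% | 1.034 |

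**4. Power with complete data.** The misfit is the same in both arms, so it does not move the estimate; it only inflates the reported SE. Power is about Φ(2.80 - 1.96k): 79.2% for A and 78.1% for B. Simulation with a random intercept gave 77-79% for the planned model against 79-80% with visit as a factor. By the same reasoning, type I error is 2[1-Φ(1.96k)]: 4.7% for A and 4.3% for B, which is below nominal.

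**5. Bias under unequal dropout, no treatment effect.** Take curve B, with 8 versus 2 of 25 leaving after week 4. A completer's fitted slope is 0.2625/0.5475 = 0.479 with weight 0.5475. An early leaver's slope is 0.5/0.4 = 1.25 with weight 0.08.

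- Arm losing 8: (17 x 0.5475 x 0.479 + 8 x 0.08 x 1.25)/(17 x 0.5475 + 8 x 0.08) = 0.529.
- Arm losing 2: (23 x 0.5475 x 0.479 + 2 x 0.08 x 1.25)/(23 x 0.5475 + 2 x 0.08) = 0.489.

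The difference is about 0.040 SD. The exact generalized-least-squares expectation, which also uses between-subject information, is 0.038 for B and 0.022 for A. Against an SE of 0.230 these are about 0.16 and 0.10 SE. With 5 versus 5 leaving, the bias is zero. With visit as a factor it is zero in every pattern tried.

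**6. Sensitivity.**

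- *Larger gain.* With 1.0 SD all by week 4, simulated power is 70% against 79% with the factor (mean SE 0.265 against 0.234).
- *Random slope, gain 1.0 SD.* SE is 0.261 against 0.256 with 75% of the gain by week 4, and 0.275 against 0.256 with all of it by then.
- *Unstructured covariance, complete data, gain 0.5 SD by week 4.* SE is 0.2259 and power 78.75% under both models.
- *Type I error.* With gains of 0.6-1.0 SD and dropout of 5 versus 5 or 8 versus 2, the planned model rejected in 2.5-5.7% of null simulations.
- *Truly linear trend.* SE is 0.233 under both models.

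**The case against.** The case on the other side is substantial, and most of it stands as a limit on size.

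- **Covariance.** The exchangeable structure appears in the power formula, not in the analysis specification. Under a random slope the loss shrinks; under an unstructured covariance with complete data it can vanish. This stands: the loss of precision is conditional.
- **Text.** The plan assumes linearity and only explores alternatives. Fast learning to a similar ceiling may describe one arm overtaking the other, rather than a bend common to both. The practice-effect remark gives no curve. This stands: front-loading is plausible but not established.
- **Dropout.** The plan expects the same attrition in both groups, and Study Procedures settles lozenge tolerability before the first outcome session, so most intolerance should remove people before they contribute slope data. Withdrawal of Participants does allow later withdrawal for nicotine effects, but nothing indicates 8 versus 2.
- **Secondary model.** Categorical time would reveal a bend. It would not change the primary test.

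Two stronger readings are tempting. A reader might infer that the straight line manufactures a nicotine effect. The documents do not support this: there is no bias with equal dropout, the direction depends on which arm loses more people, and simulated type I error stayed at 2.5-5.7%. A reader might also infer a large loss because the MCCB is reliable. But the plan already bases r=0.7 on that reliability. At r=0.9 the relative inflation is larger (8-21%), yet at a fixed d=0.56 under curve B the absolute power loss is smaller: 98.6% to 97.7%, against 66.7% to 64.3% at r=0.7.

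**Conclusion.** The point holds as a modest, conditional inefficiency. It is not a flaw that invalidates the primary test. The plan ties the shared trend to a straight line while naming two reasons why it might bend, and neither the secondary model nor the responder analysis protects the primary comparison.

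Under an exchangeable covariance, r=0.7 and an assumed front-loaded gain of 0.5 SD, the cost is 3-7% in residual variance and about 1-3 points of power, with the test erring on the conservative side. The loss is larger for a larger gain and depends on the covariance structure finally fitted. The dropout bias of 0.02-0.04 SD needs both a front-loaded trend and a marked imbalance after week 4. Low priority, but worth taking because the remedy is almost free.

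**What to change.** Replace the primary model with: OCM = visit (factor: weeks 0, 4, 7, 10) + treatment + treatment x time (linear). Keep the linear treatment x time coefficient as the single-degree-of-freedom primary test. State the covariance structure in the same sentence, since the size of the gain depends on it.

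The hypothesis, the estimated slope difference and its reporting do not change. The cost is one line of analysis wording, to be settled before unblinding, and 2 more of about 118 within-subject degrees of freedom (40 subjects x 3, less the 2 slope terms). There is no measurable loss if the shared trend is truly linear. The secondary categorical-time model can stay as planned.

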- 2 * Discuss the research design including but not limited to such issues as: probability of group assignment, potential for subject to be randomized to placebo group, use of control subjects, etc.:

Volunteers with a DSM-IV diagnosis of schizophrenia or schizoaffective disorder will be recruited, screened, and allocated in a double-blind manner to either the Nicotine Group or the Placebo Group. All participants will be asked to perform 10 weeks of cognitive remediation training (Posit Science, Duncan, SC), with daily training sessions Monday through Friday. On Mondays and Thursdays, all participants receive a lozenge 20 min prior to the training. In the Nicotine Group, the lozenge will contain 2 or 4 mg of nicotine, depending on smoking status. In the Placebo Group, the lozenge will be a matched placebo.

Outcome measures (OCMs) are assessed on Wednesdays in week 0 (day before training starts), weeks 4, 7 and 10 (after the training session), and week 14 (four weeks after training ends). OCMs are assessed on a non-drug day (Wed) because we are not studying the acute effects of nicotine but nicotine-induced enhancement of longer-term training effects.

- 3 * Describe the relevant prior experience and gaps in current knowledge. Describe any relevant preliminary data:

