Volunteers who provide Informed Consent will be screened for all Inclusion/Exclusion criteria. SCREENING will include: - Verification of age. - The SCID, to determine the presence/absence of current psychiatric conditions. For most patients, a SCID will have already been obtained and does not need to be repeated. - Medical history targeted at the cardiovascular, neurological, cognitive and other exclusion criteria. - Blood pressure and heart-rate reading. - ECG (12-lead with 3-5 minute rhythm strip). Exclusionary conditions documented on ECG include: Wolfe Parkinson White syndrome Myocardial ischemia and infarction Complete left bundle branch block PR interval <120 ms or >200 ms Prolonged QT interval (corrected) >500 ms Cardiac arrhythmias as defined by PACs >3 per min or PVCs >1 per min - Urine drug test, as a possible indication for substance abuse or dependence (may be repeated at any time during the study if intoxication is suspected) - Alcohol breathalyzer test, as a possible indication for alcohol abuse or dependence (may be repeated at any time during the study if intoxication is suspected) - Urine pregnancy test for females (also performed at the beginning of the cognitive training phase, and every two weeks thereafter) - Targeted questions about smoking history and motivation to stop smoking - Breath CO reading, as an indicator of smoking status and frequency - Listing of all currently taken medication - Vision test - The Addiction Severity Index - Drug and Alcohol Use subscale as an indicator for substance abuse or dependence. - The Wechsler Abbreviated Scale of Intelligence (WASI), as an indicator for possible mental retardation. Volunteers who pass the screening will be randomized to either the nicotine group or the placebo group. Randomization will be performed by the MPRC's biostatistician, [name], upon receiving a randomization request from the research assistant coordinating the study or a study investigator. Participants are then scheduled for a first NICOTINE EXPOSURE SESSION. In this session, participants will consume a nicotine lozenge (2 mg for non-smokers, 4 mg for smokers) if they have been randomized to the nicotine group and a placebo lozenge if they have been randomized to the placebo group. The number of smokers will be counterbalanced between the nicotine and placebo group. Participants will be instructed not to eat or drink within 15 min prior to or while consuming the lozenge. Participants are asked to report any adverse effects as soon as noted and to rate their subjective state immediately before the lozenge and every 30 min thereafter (see Side-Effects Checklist under "Additional Documents"). At this time, an investigator will also take their blood pressure and heart rate. The adverse effects of nicotine develop rapid tolerance. If any adverse effects are observed that are greater than "mild" and were not present pre-lozenge, the participant will undergo another lozenge exposure session on a separate day before starting the study. This may be repeated up to 4 times. Once both the participant and the investigator judge that any untoward effects of the lozenge are mild and tolerable and will not interfere with the cognitive training, the first outcome measurement session is scheduled, and the daily training sessions will commence the day after. A smoker who cannot tolerate the 4-mg lozenge may be dosed with a 2-mg lozenge in the cognitive training phase (the study would be single-blind for this subject). A participant who cannot tolerate the 2-mg lozenge even after repeated attempts will be excluded from the study. Participants who with the 2 mg lozenge display a rise in blood pressure by >20 mm Hg relative to pre-lozenge, a rise in HR to >120, or vomiting, will also be excluded from the study. OUTCOME MEASUREMENTS will be performed before the training begins, and approximately every 4 weeks after that until 4 weeks after the training ends. During the training phase, the outcome measurements will be performed AFTER completion of the daily cognitive training session. We will always schedule at least 1 hour between training and the outcome measurement, during which the participant can rest or have lunch. Outcome assessments are: a) The MATRICS Consensus Cognitive Battery (MCCB), an FDA-approved assessment tool for trials of cognition-enhancing treatments in PSZ. The battery measures 7 domains: speed of processing, attention/vigilance, working memory (verbal, nonverbal), verbal learning, reasoning, problem solving, and social cognition. b) The progression in training exercise parameters since the last outcome measurement time point (see below). c) Symptom assessments: the Brief Psychiatric Rating Scale, Scale for Assessment of Negative Symptoms, and Calgary Depression Scale. d) The state version of the State-Trait Anxiety Inventory. e) The Cogstate computerized assessment battery. Further outcome measures taken only pre- and post-training (week 0 and 10): a) Working Memory capacity (K) derived from a computerized change localization task. Two to four colored squares are shown for 100 ms. After a delay, they reappear and the task is to click on the one square that has changed color. b) The UCSD Performance-Based Skills Assessment, measuring ability to perform real-life tasks by standardized role-play. c) Quality of Life Scale, measuring functional outcome and quality of life in PSZ. d) The trait version of the State-Trait Anxiety Inventory. e) The Cognitive Assessment Interview (CAI), a brief interview-based measure of daily life cognitive functioning, administered to both the PSZ and a close relative or caretaker. The CAI was developed based on two longer scales and assesses 10 items related to working memory, attention/vigilance, learning/memory, problem solving, processing speed, and social cognition, with little or no repetition effects. f) Questionnaire asking each participant to guess their treatment group (nicotine or placebo; post-training only). g) A 5-ml venous blood sample will be taken, centrifuged, and frozen. At the completion of the study, the samples will be analyzed for TNF alpha, and potentially other inflammatory markers, to test whether repeated nicotine exposure may have anti-inflammatory effects that may be related to any effects on cognitive outcome measures. If a participant declines to have their blood drawn but are otherwise eligible for the study, they may participate without the blood draws. COGNITIVE REMEDIATION TRAINING PROCEDURE Prior to each daily training session, participants will complete a brief checklist about their caffeine and cigarette consumption today (how much/how many), when they last smoked/drank a caffeinated beverage, how many hours of sleep they got the previous night, when they last drank alcohol and how much. Prior to each session, smokers also provide a CO breathalyzer reading. Each training session will include ~30 min of auditory and ~30 min of visual training exercises by Posit Science, in a counterbalanced manner. The auditory training consists of six exercises: fast and accurate discrimination of (1) sound frequencies, (2) phonemes and (3) syllables, and recall of syllables, (4) sequences of syllables, (5) multi-element verbal instructions, and (6) details of a narrative. The visual training consists of five exercises designed to (1) improve visual precision, (2) increase capacity to divide visual attention, (3) improve visual memory, (4) expand field of view, and (5) increase visual processing speed. The programs train the fine-tuned and differentiated processing of sensory input and engage attention, working memory and/or executive processes. To induce the right level of challenge and promote engagement and motivation, task difficulty adjusts continuously to user performance to maintain ~85% correct responses (which are rewarded by auditory and visual feedback). Adjustable parameters include presentation time, interstimulus interval, physical similarity between stimuli, stimulus eccentricity, number of stimuli, and information complexity. Some exercises provide a progress summary of these parameters after each session. These values will be recorded on all training days. Other exercises provide a separate assessment tool to monitor progress. These assessments will be performed every 4 weeks with other outcome measurements. Every Monday and Thursday, a nicotine or placebo lozenge, encapsulated in gelatin, will be administered 20 minutes prior to the beginning of the training. Nicotine lozenges are mint-flavored "mini" lozenges, placebo lozenges are size-matched breath mints. Smokers in the Nicotine Group will receive a 4-mg lozenge. Plasma concentrations after this dose resemble the "nicotine boost" typically seen in dependent smokers by smoking a single cigarette (~1 ng/ml). Non-smokers in the Nicotine Group will receive a 2-mg lozenge because 4 mg in nicotine-naïve individuals would likely result in low tolerability. Participants will be instructed not to eat or drink within 15 min prior to or while consuming their lozenge. Participants may perform the training sessions at the Maryland Psychiatric Research Center (MPRC), or, in a separate room, at their day program or inpatient unit if applicable (a research associate would visit daily with laptop, lozenge or assessment instruments). The lozenge would be administered by a local nurse or other medical professional if possible, else these sessions would be performed at the MPRC. Participants who are unable to come to the MPRC or day program to complete the training (e.g., because they work or live too far away) may perform the exercises at home if they have internet access and their clinician or study staff considers them capable of doing so reliably. The CO measurement would be omitted on home-training days, and participants would be given the questionnaire about how much they slept and how much caffeine or alcohol they consumed to complete by themselves at home. On the two weekly lozenge days, they would be scheduled to perform the training at the MPRC. Under select circumstances, when the patient is unable to come to the MPRC on those days, too, they would be instructed to take the lozenge at home, following doctor's orders. A study team member would call them at home and

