- The WASI Vocabulary and Matrix Reasoning subtests to assess intellectual competence
- The MATRICS battery
- Visual Acuity Test to test inclusion criterion of normal vision
- Ishihara's Test for Color Deficiency
- Change localization task, to test working memory capacity
- Tests to assess progress on the Posit Science cognitive remediation training exercises
- Cogstate computerized assessment battery

- 2 * Describe procedures related to all testing:

-The WASI subtests are paper and pencil tests and will be administered by an investigator during one of the first three visits (screening, nicotine exposure session prior to lozenge administration, or first outcome measurement session). The setting is a private room, seated at a table.

-The MATRICS battery is a collection of co-normed measures of verbal and visual episodic and working memory, processing speed, problem solving, sustained attention, and social cognition. Most tests are paper and pencil tests done in interaction with the investigator. One subscale involves performing a ~10-min Continuing Performance Task on a computer. The MATRICS battery will be performed every four weeks in each outcome measurement session.

-The Visual Acuity Test consists of reading a sequence of letters with one eye covered at a certain distance from the chart. Performed during screening.

-The Ishihara Test consists of reading green numbers against a red background or vice versa, or finger-tracing a line. Performed during screening.

-The Change localization task is performed at a computer. One or four colored squares are presented for ~200 ms, and after a ~1-s delay, they reappear. The task is to identify the square that has changed color. Performed on outcome measurement days just before and just after the cognitive training (weeks 0 and 10).

-The Posit Science exercises are performed on a computer. Some exercises provide a progress summary of these parameters after each session, which will be recorded. Other exercises provide a separate assessment tool to monitor progress, which will be performed on outcome measurement days every three to four weeks, together with other outcome measurements (see "Study Procedures").

- The Cogstate battery is performed on a computer and comprises tests of processing speed, attention, learning and memory, and higher cognitive functions.

- 3 * Upload relevant testing materials:

Name	Created	Modified Date
Visual Acuity scoring form	12/11/2013 11:01 AM	12/11/2013 11:01 AM

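### The detectable effect for Hypothesis 1a is understated: Var(t)=0.185 does not fit the planned visits, which give d of about 0.66 rather than 0.56, and about 67% power at 0.56

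*Combined protocol and SAP*

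**What the plan says.** Sample Size and Data Analysis, item 1, tests Hypothesis 1a with a mixed model in which time is linear and continuous, and the treatment-by-time interaction carries the comparison. The detectable effect comes from a formula printed as "d = [2(z_a + z_b)2(1-r)/bnVar(t)]/2". There d is the difference in slopes divided by the SD of the outcome, b=4 visits, and the normal quantiles are 1.96 and 0.84 (two-sided 0.05, power 0.80). The time input is "Var(t)=0.185$ is the within-subject variance of the visit times". The result is "With $n=20$ completers per group, $d=0.56$ (a medium effect size) will be detectable for $r=0.7", where r follows the reliability of the MCCB, the primary outcome.

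The text adds: "Although we will include subjects with partial data, the effect size detectable was estimated conservatively". On enrolment it says "we expect having to enroll 25 subjects per group into the training".

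Justification, Objective, & Research Design, item 2, sets the outcome visits at week 0, then "weeks 4, 7 and 10 (after the training session), and week 14". Item 1 of the sample-size section brings week 14 in only for a secondary model with categorical time. The four visits behind the primary slope are therefore weeks 0, 4, 7 and 10.

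**The concern.** The precision of a slope depends on how widely the visits are spread over time. In this formula, b × Var(t) stands for the sum of squared deviations of the visit times, so Var(t) must be computed with divisor b. The figure 0.185 is about one third too large for weeks 0, 4, 7 and 10 on a scale where the training period is 1. An overstated spread makes the design look more sensitive than it is.

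This is the only power statement for the primary hypothesis and the primary outcome. If it is wrong, the chance of missing an effect of 0.56 is about 33% rather than 20%, and a null result would be credited with sensitivity that the design does not have.

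**Working it through.** **Inputs.** From Sample Size and Data Analysis, item 1: n=20 per group, r=0.7, b=4, quantiles 1.96+0.84=2.80, Var(t)=0.185. From Justification, Objective, & Research Design, item 2: visits at weeks 0, 4, 7 and 10. From Study Procedures, item 3: 10 weeks of training. Assumption: 10 weeks = 1 time unit (tested in step 4).

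**Formula.** The exponents were lost in the printed text. I read it as d = √[2(zₐ+z_b)²(1−r)/(b·n·Var(t))], that is, d = 2.80 × SE with SE = √[2(1−r)/(n·SS)] and SS = b·Var(t). Power at a given d is Φ(d/SE − 1.96).

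**Step 1, the plan's figure.** SS = 4 × 0.185 = 0.74. SE = √[0.6/(20 × 0.74)] = 0.2013, so d = 0.564, and power at 0.56 is 79.4%. This matches the stated 0.56 and confirms the reading of the formula.

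**Step 2, the planned visits.** The times are 0, 0.4, 0.7 and 1.0, with mean 0.525. SS = 0.2756 + 0.0156 + 0.0306 + 0.2256 = 0.5475, so Var(t) = 0.5475/4 = 0.137. SE = √[0.6/(20 × 0.5475)] = 0.2341, giving **d = 0.655**. Power at 0.56 = Φ(0.56/0.2341 − 1.96) = **66.7%**. Generalised least squares for the planned model, with constant within-subject correlation 0.7, gives the same SE and power. About 28 completers per group (27.4 rounded up) would be needed for 80% power at 0.56.

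**Step 3, where 0.185 may come from (inference).** Four equally spaced visits on a 0–1 scale have SS = 5/9. Divided by 3 this is 5/27 = 0.1852; divided by 4 it is 0.1389. The actual weeks with divisor 3 give 0.1825. The figure therefore looks like a divisor-3 variance that was then multiplied by 4.

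**Step 4, the time unit.** For weeks 0, 4, 7 and 10:

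| Unit (weeks) | Var(t), divisor 4 | Detectable d per unit | Detectable difference over 10 weeks (SD) |
|---|---|---|---|
| 1 | 13.69 | 0.066 | 0.655 |
| 4 | 0.855 | 0.262 | 0.655 |
| 8.6 | 0.185 | 0.564 | 0.655 |
| 10 | 0.137 | 0.655 | 0.655 |

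Only a unit of about 8.6 weeks yields 0.185 with divisor 4, and then 0.56 is not the difference over the training period.

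**Step 5, other schedules and counts** (r=0.7, unit 10 weeks):

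| Scenario | d at 80% power | Power at 0.56 |
|---|---|---|
| 20 completers, equally spaced visits | 0.651 | 67% |
| 20 completers, weeks 0, 4, 8, 10 | 0.631 | 70% |
| 20 completers + 5 with weeks 0 and 4 | 0.640 | 69% |
| 20 completers + 5 with weeks 0, 4 and 7 | 0.620 | 71% |
| 25 completers, weeks 0, 4, 7, 10 | 0.586 | 76% |

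**Step 6, sensitivity to r** (20 completers, planned visits): r=0.6 gives d=0.76, r=0.7 gives 0.66, and r=0.8 gives 0.54. A detectable 0.56 needs r of about 0.78.

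**The case against.** The strongest objection is that d is a rate and no time unit is given. With a unit of about two months, 0.185 is roughly right and 0.56 is a valid per-unit slope difference. The source cited for the formula is not in the supplied reference list, so the intended unit cannot be settled. It stands that the unit is undefined and that the divisor explanation is an inference. It does not rescue the figure: no document mentions such a unit, and the detectable difference at the end of training remains 0.655 SD.

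Second, the schedule is described loosely elsewhere. The Testing section says "The MATRICS battery will be performed every four weeks in each outcome measurement session", and Study Procedures lets visits slip. Weeks 0, 4, 8 and 12 in 10-week units would give d=0.54 and 82% power. That schedule runs past the 10 weeks of training and conflicts with the stated weeks. A final visit slipping to week 11 gives 74% (weeks 0, 4, 7, 11) or 76% (weeks 0, 4, 8, 11) if it applied to every participant.

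Third, the planned analysis uses partial data, so the completers-only 67% is the low end. That is fair, and 69–71% describes the planned analysis better if five per group drop out. It is still short of 80%.

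Fourth, r=0.7 is an assumption, and a somewhat higher r would restore 0.56. That is true, but the plan's claim is made at 0.7.

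Finally, n was not derived from 0.56, so the trial's size does not rest on the error. This limits the consequence to how the trial's sensitivity is described.

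**Conclusion.** The concern holds. With the plan's own n, r, alpha and visit weeks, the detectable difference over the 10-week training period is 0.655 SD, not 0.56. Power at 0.56 is 66.7% for 20 completers per group, 69–71% with plausible partial data, and 76% if all 25 per group complete. The result assumes a linear time effect, constant within-subject correlation of 0.7 and visits at weeks 0, 4, 7 and 10. The 10-week unit affects how d is expressed, not the week-10 difference. The explanation for 0.185 is probable rather than proven, and the conclusion does not depend on it. The statement should be corrected because it is the sole power claim for the primary hypothesis.

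**What to change.** In Sample Size and Data Analysis, item 1:

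- State that one time unit is the 10-week training period and that Var(t) uses divisor b.
- Replace 0.185 with 0.137, computed from weeks 0, 4, 7 and 10.
- Restate the result, for example: with 20 completers per group and r=0.7, a difference in slopes of 0.66 SD per 10-week training period is detectable with 80% power; power at 0.56 is about 67% counting completers only.
- Keep the description of the estimate as conservative only if the text makes clear that it refers to leaving out partial data.

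The change is to wording only. No patients, visits or analyses are added; the cost is a less favourable stated figure.
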